6.2 Medical History

Participants for the present study will be primarily recruited through the primary investigator's medical practice. As patients, participants will have completed intake forms including medical history and any relevant neurological evaluations previously completed. All participants will be required to report on all previous medications for 30 days prior to the study, as well as for the duration of the study. Memantine and acetylcholine esterase inhibitors, donepezil and rivastigmine, are permitted as co-medications in the proposed study. Per the Investigator's Brochure, no drug-drug PK interactions with co-medications memantine, donepezil, galantamine and rivastigmine are expected with the proposed dose of 20 mg BID. As noted in the exclusion criteria, patients with contraindications for lumbar puncture (such as bleeding abnormalities requiring the use of anticoagulant medications) will not be permitted into the study. Additionally, participants with any active cancer requiring chemotherapy will not be permitted to take part in the study.

6.3 Physical Examination

The Principal Investigator (PI) and study doctor will be responsible for performing physical examinations of the participants prior to study participation. As routine practice in the clinic, patients will have filled out a complete demographic questionnaire, undergone a physical examination at first visit, and have had their vital signs recorded. The nervous system is the primary body system to be included in the examination and routine demographics including height and weight will be noted.

6.4 Vital Signs

The PI will be responsible for performing the physical examination of the participant. During in-person study visits, resting heart rate, blood pressure, and temperature will be measured. Blood pressure and heart rate will be monitored using the same machine and same arm upon each visit. The physical exam will not include a pelvic, rectal, or breast exam. Additionally, participants will answer a health and medication questionnaire, disclosing relevant medical history and past or present medications.

6.5 Electrocardiography and Continuous Telemetry Monitoring

6.5.1 *12-Lead Electrocardiograms*

ECG monitoring is not required during this study but may be requested by the study doctor.

6.5.2 *Continuous Holter Monitoring*

A continuous Holter monitor is not required during this study but may be requested by the study doctor.

6.6 Clinical Laboratory Tests

6.6.1 *Laboratory Parameters*

Participants will be in a seated or supine position during blood collection. Clinical laboratory tests (to be collected at baseline, 2 weeks, 4 weeks, 8 weeks, and completion) include the following:

Collected at Baseline and Completion:

Hematology:

- Complete Blood Count with Differential
- Hematocrit (Hct)
- Hemoglobin (Hgb)
- Hemoglobin A1c
- Mean corpuscular hemoglobin (MCH)
- Mean corpuscular hemoglobin concentration (MCHC)
- Mean corpuscular volume (MCV)
- Platelet count
- Red blood cell (RBC) count
- White blood cell (WBC) count with differential

Inflammatory Markers:

- Appearance
- Chlamydia pneumoniae serology (IgG/IgM)
- TNF (tumor necrosis factor)
- Cytokine Panel 13
- hsCRP (highly sensitive c-reactive protein)
- ESR (erythrocyte sedimentation rate)
- HSV (herpes simplex virus serology, IgG/IgM)
- CMV (cytomegalovirus serology, IgG/IgM)
- Helicobacter pylori - breath test
- Lymphocyte Subset Panel 4: CD4 & CD8
- Vasoactive intestinal peptide

Serum Chemistry:

- Albumin (ALB)
- Alkaline phosphatase (ALK-P)
- Alanine aminotransferase (ALT; SGPT)
- Amylase
- Aspartate aminotransferase (AST; SGOT)
- Blood urea nitrogen (BUN)
- Calcium (Ca)
- Carbon dioxide (CO₂)
- Chloride (Cl)
- Creatinine
- Creatine kinase and subtypes
- Gamma-glutamyl transferase (GGT)
- Globulin
- Glucose
- Lactate dehydrogenase (LDH)
- Lipase
- Phosphorus
- Potassium (K)
- Sodium (Na)
- Total bilirubin
- Direct bilirubin
- Total protein
- Triglycerides
- Troponins
- Uric acid
- Zinc
- Ethanolamine phospholipids

- TGF -b1	- Ethanolamine plasmalogens
- Alpha Melanocyte stimulating hormone	- DHA ethanolamine phospholipids
- Beta Melanocyte Stimulating Hormone	- Choline phospholipids
- C4A	- Choline plasmalogens
- ACTH, Plasma (Adrenocorticotrophic hormone)	- DHA choline phospholipids
- Anti-gliadin antibodies	- Dietary fatty acids (omega-3, omega-6, omega-9, OA, LA, AA)
- VEGF	- Iron
- Gastrointestinal tract acids (GTAs)	- Methyltransferase/choline system
- MMP-9	- Phosphatidylethanolamines
- Quantitative immunoglobulins	- Phosphatidylcholine
- Lyme Antibody	- Sphingomyelins
- Bartonella quintana antibodies	- Ceramides
Urinalysis, complete	- Homocysteine
- Glucose	- Elongase 5 activity
- pH	- Peroxisomal function
- Bilirubin	- DHA, EPA
- Ketones	- Triacylglycerols
- Nitrite	- Cholesterol total (Fasting)
- Uric acid	- HDL (Fasting)
- WBC, RBC, epithelial cell count	- LDL (Fasting)
	-

Collected at Weeks 2, 4, and 8:

- Amylase
- Lipase
- Potassium
- Calcium
- Complete Blood Count (CBC) with Differential

- Hemoglobin A1c
- Glucose
- Alanine aminotransferase (ALT;
SGPT)
- Aspartate aminotransferase (AST;
SGOT)
- Creatine Phosphokinase
- Cholesterol total (Fasting)
- HDL (Fasting)
- LDL (Fasting)
- Triglycerides (Fasting)

Collected Prior to Lumbar Puncture
Procedure:

- Prothrombin time
- International Normalized Ratio
- Partial thromboplastin time
- Platelet count

6.6.2 *Sample Collection, Storage, and Shipping*

After screening, laboratory orders will be written by the study physician which can be taken to any Quest Diagnostics, LabCorp, or any other clinical laboratory. Additional serum will be drawn at the primary study site and sent for analysis to Prodrome Sciences ([name]). Samples will be shipped on ice and labeled adhering to federal biological substance shipping regulations.

6.7 *Dispensing Study Drug*

The Manufacturer will supply sufficient quantities of the study formulation for the following: (1) completion of this study and (2) retention, as per applicable regulations. All drug supplies provided for this study will be stored in a secure area with restricted access, under controlled storage conditions described in the product package labelling, unless otherwise instructed per protocol.

Records will be made of receipt and dispensing of NE3107 supplied. It is the responsibility of the Manufacturer to ensure that all drug supplies provided for the study are manufactured under current Good Manufacturing Practices (cGMP) and are suitable for human use.

6.8 Pharmacokinetic Assessments

NE3107 is an orally bioavailable, blood-brain barrier permeable, uncharged, low molecular weight molecule (MW 330.46, LogD = 2), poly-hydroxylated synthetic derivative of the C-19 adrenal steroid series. *In vitro* studies have been conducted to measure membrane transport, active efflux/P-gp interaction, hepatic stability, CYP inhibition, and CYP induction. Numerous pharmacokinetics (PK) studies of NE3107 have been performed in various animal species using single and multiple doses exploring different routes of administration. Oral NE3107 PK studies have been performed in mice, rats, rabbits, dogs, and monkeys. PK following parenteral administration in support of absolute oral availability measurements has also been studied in mice and monkeys. Numerous non-GLP PK studies have been conducted in mice to support formulation development, but only a few that are most relevant to the clinical drug product are summarized below. GLP PK studies have been conducted in rats (Sprague Dawley) and dogs (beagles) concurrent with toxicology studies. No stand-alone single dose GLP PK studies were conducted. All GLP PK studies in rats and dogs have been conducted as part of multiple dose toxicology studies. PK studies have been conducted in rat toxicology studies with oral gavage of NE3107 formulated as an aqueous solution in 30% sulfobutyl ether-cyclodextrin (formulation code HERF202) and as an aqueous suspension of micronized NE3107 (vehicle contained 1 mg/mL sodium carboxymethyl cellulose [CMC], 9 mg/mL sodium chloride, and 20 mg/mL polysorbate-80, 0.5 mg/mL phenol (formulation code HERF405). PK studies have been conducted in dogs with soluble NE3107 (HERF202) and with micronized NE3107 formulated in hard gelatin capsules containing sodium lauryl sulfate, polyplasdone XL 10, microcrystalline cellulose, and magnesium stearate in proportions similar to the NE3107 clinical capsule formulation used for all human studies. NE3107 exists as a single polymorph in all lots of drug substance. All PK studies of crystalline NE3107 used the same polymorph, which is the same polymorph used in human studies.

6.9 Adverse Events Assessments

Following all of the inclusion/exclusion criteria may help to reduce the occurrence of severe adverse reactions. Both the principal investigator and sub-investigators are medical doctors, and are licensed in the state of California, and are in close communication the primary IND holder (BioVie, Inc.) regarding safety monitoring. We will be performing routine patient calls and standard monitoring of side effects due to these medications, as discussed elsewhere in this report. Following these guidelines, side effects can be identified early enough to mitigate any significant or permanent side effects.

6.9.1 *Timing*

NE3107 has no specific dose-limiting toxicity to guide stopping criteria for laboratory values for safety monitoring. Abnormal lab values will be reviewed in the context of patient safety and potential relationship with NE3107 treatment and NE3107 prior safety data. The investigator may terminate a patient's participation in the trial due to abnormal lab values irrespective the lab values potential relationship with NE3107 treatment.

6.9.2 *Severity*

The term "severe" describes the intensity (severity) of a specific event; the event itself, however, may be of relatively minor medical significance (such as severe headache). This means it is not the same as "serious", which is based on patient/event outcome or action criteria usually associated with events that pose a threat to a patient's life or functioning.

The severity of all AEs will be graded by the PI/Sub-Investigator or a medical qualified delegate according to the following definitions:

Mild: Adverse event resulting in discomfort, but not sufficient to cause interference in normal daily activities.

Moderate: Adverse event resulting in discomfort that is sufficient to cause interference in daily activities.

Severe: Adverse event resulting in discomfort causing an inability to carry out daily activities.

6.9.3 *Relationship*

The PI/Sub-Investigator will assess the relationship of all adverse reactions to NE3107 using the following scale:

Probable: A clinical event, including laboratory test abnormality, with a reasonable time sequence to drug administration, unlikely to be attributed to concurrent disease or other drugs or chemicals, and which follows a clinically reasonable response on withdrawal.

Possible: A clinical event, including laboratory test abnormality, with a reasonable time sequence to drug administration, but which could also be explained by concurrent disease or other drugs or chemicals. Information on drug withdrawal may be lacking or unclear.

Unlikely: A clinical event, including laboratory test abnormality, with a temporal relationship to drug administration which makes a causal relationship improbable, and which other drugs, chemicals or underlying disease provide plausible explanation.

Unrelated: This category is applicable to AEs which are judged to be clearly and incontrovertibly due to extraneous causes (diseases, environment, etc.) and do not meet the criteria for drug relationship listed for the above-mentioned conditions.

All AEs will be evaluated by the PI/Sub-Investigator, who must approve the subject for subsequent dosing.

Any AEs, whether serious or non-serious, will be monitored throughout the study and followed to resolution, when possible, regardless of whether the subject is still participating in the study.

6.9.4 *Expectedness*

The principal investigator and study doctor will be responsible for determining whether an SAE is expected or unexpected as per drug labels. An adverse event will be considered unexpected if the nature, severity, or frequency of the event is not consistent with the risk information previously described for the intervention.

6.9.5 *Clinical Significance*

Clinical laboratory data collected during the course of the study, which exceeds or drops below the acceptable limits for the participant population and which, based on baseline values, are considered by the Investigator to be clinically significant, will be reported as an AE. If clinically significant abnormal laboratory values lead to, or are associated with clinical symptom(s), they will be reported as an AE.

6.9.6 *Serious Adverse Events*

6.9.6.1 Definition

A serious adverse event (SAE) is defined by federal regulation as any AE occurring at any dose that results in any of the following outcomes: death, life-threatening AE, hospitalization or prolongation of existing hospitalization, a persistent or significant disability/incapacity, or a congenital anomaly/birth defect.

Important medical events that may not result in death, be life threatening, or require hospitalization may be considered an SAE when, based upon appropriate medical judgment, they may jeopardize the subject and may require medical or surgical intervention to prevent one of the outcomes listed in this definition. Examples of such medical events include allergic bronchospasm requiring intensive treatment in an emergency room or at home, blood dyscrasias or convulsions that do not result in inpatient hospitalization, or the development of drug dependency or drug abuse.

6.9.6.2 Reporting Serious Adverse Events

All serious adverse events (SAEs), whether or not the event is deemed study drug- related, will be reported to the Sponsor by telephone within 24 hours of becoming aware of SAE, followed by a written report within five business days.

Reports of all SAEs will be communicated as soon as possible to the appropriate Institutional Review Board (IRB) and/or reported in accordance with local laws and regulations.

6.10 Concomitant Medication Assessments

Participant medications will be assessed by PI and study staff upon initial screening for the study. Participants will be admitted as a patient under the PI and will fill out a comprehensive demographics form (including past and present medications), which will be subsequently stored in the patient's chart. Concomitant medications will be stabilized for 30 days prior to enrollment in the study protocol.

6.11 Removal of Participants from the Trial or Study Drug

The investigator may withdraw a subject from trial participation for any of the following reasons:

- A protocol violation occurs,
- A serious or intolerable adverse event occurs,
- A clinically significant change in a laboratory parameter occurs,
- The sponsor or investigator terminates the study, or
- The subject requests to be discontinued from the study.

7 STUDY ACTIVITIES

7.1 Screening Visit & Baseline Measure Collection (Days -10 to -1)

Study Screening may take place during an initial visit with study staff to obtain the following assessments, which will be recorded in participant's source documentation/medical record and on the Case Report Form (CRF):

- Participant ID number generation
- Demographic information
- Medical history
- Vital signs
- Height, weight, and calculation of BMI
- Prior/concomitant medications (must be stabilized for 30 days prior to study entry)
- Quick Dementia Rating Scale (QDRS)
- Clinical Dementia Rating (CDR) score, derived from QDRS
- Confirming eligibility (no exclusionary criteria are met)

Baseline measure acquisition may take place over the subsequent 9 days prior to starting the active study intervention, which will include the following:

- Lumbar puncture to test for AB42 and Tau protein levels
- APoE genotyping
- Advanced brain MRI
 - T1, T2, SWI, Neuromelanin, BOLD, ASL perfusion, DTI-NODDI, MRS of the precuneus
- Cognitive examination including:
 - Montreal Cognitive Assessment (MoCA)
 - Mini-mental Status Examination (MMSE)
 - Alzheimer's Disease Assessment Scale (ADAS-Cog12)
- Blood tests for:
 - Complete blood count + diff
 - Creatinine clearance
 - Thyroid hormone panel
 - Electrolytes
 - Inflammatory markers (hsCRP, TNF α , CD4, CD8, absolute neutrophils)

- Quantitative immunoglobulins
- Total and direct bilirubin
- Hemoglobin
- ProdromeScan blood test for:
 - Phosphatidylethanolamines
 - Choline
 - Mitochondrial function

7.2 Clinic Admission (Day 0)

On Day 0, each study participant will be provided with enough NE3107 capsules to maintain a 20mg bid dosage for the three-month active intervention period. Participants will be instructed to take each dosage spaced approximately 12 hours apart.

7.3 Treatment Period (Day 1 to Day 90)

The drug under investigation is NE3107 (17a-ethynyl-androst-5-ene-3b,7b,17b-triol). NE3107 is formulated with common excipients used in oral medications in #2 hard gelatin capsules. The capsules are designed for oral administration. NE3107 capsules are stable at room temperature for at least 18 months. Stability of the capsules used in this study will be monitored by a concurrent stability study conducted by the capsule manufacturer and the holder of the primary IND, Biovie, Inc (Santa Monica, CA).

The rationale for 3-month administration is to allow sufficient time for detectable change to occur. To minimize risk, participants will be called within 24 hours following initiation of the drug and weekly thereafter, as well as meet with the study doctor 1 week after starting the NE3107 regimen and attending once-monthly visits thereafter with the principal investigator to evaluate for safety and tolerability of the study intervention for the duration of the study protocol. These visits will include evaluations of the following:

- Vital signs
- Height, weight, and calculation of BMI
- Documenting changes in concomitant medications
- Participant reports of tolerability
- Evaluation for AEs
- Assessing compliance with the study drug

Additionally, specific laboratory tests will be repeated at weeks 2, 4, and 8 to ensure safety (**6.6.1 Laboratory Parameters**). Mild, moderate, and severe adverse reactions will be reported on an ongoing basis. Previously observed adverse reactions are listed

in Table 22 of the Investigator's Brochure. Participants will be discontinued if they have moderate or severe adverse reaction ratings according to the **ICH SAE E2A**.

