4 STUDY POPULATION SELECTION

4.1 Study Population

Number of Participants

Approximately 25 participants are expected to be enrolled in this Phase II trial to evaluate longitudinal findings from multimodal MRI among the population that is being studied.

Gender of Participants

The gender distribution for this study will aim for a ratio of 50:50 men to women. This is to ensure that both men and women benefit equally from any potential efficacy of NE3107 in treating dementia and that neither men nor women are disproportionately burdened by any tolerability issues. Women who are pregnant, who may become pregnant, or who are breastfeeding will not be included in the study.

Age of Participants

The ages for the participants in this study will range from 50-89 years old. This age range was selected based on the fact that degenerative conditions that result in cognitive change occur in middle and late life.

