4.3 Exclusion Criteria

In order for a subject to be considered for this study, he/she may NOT have any of the following:

- Subjects with contraindications for lumbar puncture, such as bleeding abnormalities, use of anticoagulant medications, and local skin or spine abnormalities. *See Section 6.6.1 “Laboratory Parameters,” page 26.*

- Subjects with contraindications to magnetic resonance imaging (MRI) acquisition, including patients with non MRI-compatible pacemakers, defibrillators, or other implanted electronic devices.
- Women who are pregnant, who may become pregnant, or who are breastfeeding
- Reversible causes of cognitive impairment that explains the clinical status entirely, such as hypothyroidism, depression
- Advanced stages of any terminal illness or any active cancer that requires chemotherapy
- History of breast cancer
- Women with child-bearing potential who are not willing to use a double-barrier birth control method
- Males not willing to use a double-barrier birth control method with female sex partners with child-bearing potential
- Individuals with hepatic impairment as defined by:
 - Alanine aminotransferase (ALT) lab values $>3x$ the upper normal limit (UNL)
 - Aspartate aminotransferase (AST) lab values $>3x$ UNLOR
 - History of clinically significant liver disease in the Principal Investigator's medical judgment
- Individuals with renal impairment as defined by Creatinine clearance (Cockcroft-Gault formula) of <45 mL/min.

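### In the supplied text, the week 2, 4 and 8 safety bloods omit creatinine and BUN, so about 75 to 90 days on drug pass without a scheduled renal value; adding creatinine to those draws is a cheap improvement.

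*Combined protocol and SAP*

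**What the plan says.** - Section 7.3 (Treatment Period) states that "specific laboratory tests will be repeated at weeks 2, 4, and 8 to ensure safety" and points to section 6.6.1 for the tests concerned.
- Section 6.6.1 opens by describing the laboratory tests as "to be collected at baseline, 2 weeks, 4 weeks, 8 weeks, and completion". It then divides them under sub-headings. Creatinine and BUN stand under "Collected at Baseline and Completion". The list under "Collected at Weeks 2, 4, and 8" contains amylase, lipase, potassium, calcium, full blood count, HbA1c, glucose, ALT, AST, creatine phosphokinase, total cholesterol, HDL, LDL and triglycerides.
- Creatinine clearance is named in section 7.1 (baseline, Days -10 to -1) and section 7.5 (final visit, Day 90 ± 15), and in no visit between them.
- Section 4.3 excludes "Individuals with renal impairment as defined by Creatinine clearance (Cockcroft-Gault formula) of <45 mL/min". Section 4.1 adds: "The ages for the participants in this study will range from 50-89 years old".
- Section 6.11 gives as one ground for withdrawal: "A clinically significant change in a laboratory parameter occurs".
- Section 6.9.1 says "NE3107 has no specific dose-limiting toxicity to guide stopping criteria for laboratory values for safety monitoring".

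**The concern.** The protocol treats kidney function as relevant at entry and measures it again at the end, but schedules no measurement in between. The interim panel covers liver enzymes, pancreas, muscle, glucose, lipids and blood count. The entry whose name comes closest, creatine phosphokinase, is a muscle enzyme and says nothing direct about renal function.

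Two things are at stake. First, the withdrawal ground in section 6.11 needs a laboratory result to act on. For creatinine, no scheduled result exists until treatment is finished or nearly so, and a renal change without symptoms would not be picked up by telephone calls, vital signs or weight. Second, section 6 says that the blood samples also serve to describe what NE3107 does to laboratory values. Two creatinine values per participant can show a net change, but not when it began or whether it was transient.

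**Working it through.** The plan states no figure on this point, so there is none to reproduce. The check sets the lists side by side and then counts days.

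**Content of the panels**

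| Renal item | Baseline | Weeks 2, 4, 8 | Final visit |
|---|---|---|---|
| Creatinine (6.6.1) | yes | no | yes |
| BUN (6.6.1) | yes | no | yes |
| Creatinine clearance (7.1, 7.5) | yes | no | yes |

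The interim list has 14 entries, none of them a renal function measure. The opening line of 6.6.1 names all five time points, but its sub-headings allocate the tests. Sections 7.1, 7.3 and 7.5 agree with that allocation.

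**Inputs for the timing**
- Treatment: Day 1 to Day 90 (7.3).
- Baseline: Days -10 to -1 (7.1).
- Final visit: Day 90 ± 15, that is Day 75 to Day 105 (7.5).
- Assumption: week n falls on Day 7n, because no window is given for the interim draws. Weeks 2, 4 and 8 are then Days 14, 28 and 56.

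**Current schedule**
- Days on drug before the final renal value = min(final visit day, 90). Earliest: min(75, 90) = 75. Latest: min(105, 90) = 90.
- Calendar time between the two renal values: shortest 75 - (-1) = 76 days; longest 105 - (-10) = 115 days. This includes up to 10 days before dosing and up to 15 days after it.
- Treatment left when the final value is drawn: at most 90 - 75 = 15 days, and none from Day 90 on.
- The table of contents gives Day 91 ± 15 for the final visit. That moves the window to Days 76 to 106 and changes these figures by one day at most.

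**With creatinine added at weeks 2, 4 and 8**
- First dose to week 2: 14 - 1 = 13 days.
- Week 2 to week 4: 28 - 14 = 14 days.
- Week 4 to week 8: 56 - 28 = 28 days.
- Week 8 to the final value, on-drug part: 75 - 56 = 19 days to 90 - 56 = 34 days.
- Longest on-treatment gap: 34 days, against 75 to 90 now. Scheduled renal values per completer rise from 2 to 5.
- Added results: 3 draws × 25 participants = 75 at most.

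**Illustration only.** At fixed age, weight and sex, Cockcroft-Gault clearance is inversely proportional to creatinine. The rise that brings clearance down to 45 mL/min is therefore (entry clearance / 45) - 1. For assumed entry clearances of 50, 60 and 75 mL/min this is 11%, 33% and 67%. The entry values are assumptions and 45 mL/min is an entry limit, so crossing it triggers nothing in the protocol. The documents also give no figure for ordinary creatinine variation against which to judge an 11% rise. The conclusion does not depend on this illustration.

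**The case against.** The strongest reply is that the choice of panel is a legitimate judgement. Section 7.3 promises selected tests and 6.6.1 lists them, so the text keeps its own promise. Section 5.6 gives CYP3A4 as the main route of metabolism and describes no metabolite of concern, which points towards the liver, and ALT and AST are checked at every interim draw. Sections 1 and 3.2 report no toxicity calling for dose-response work, and 6.9.1 is to the same effect. Section 9.6 says that blood tests will follow standard practice, which leaves room for tests beyond the list. Participants are also called within 24 hours and then weekly, and are seen at week 1 and monthly. The Investigator's Brochure, not supplied, may explain the panel.

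Most of this stands as a reason for low priority. It does not supply a scheduled renal value: section 9.6 names no analyte, interim potassium is at best indirect, and the calls and visits measure no renal function. The absence of a known target organ is a weak reason to leave out a basic organ-function test, particularly as section 3.2 sets 20 mg twice daily against 2, 5 and 10 mg twice daily in the earlier trial it cites and acknowledges highly variable exposure.

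Three stronger readings are tempting, and the documents do not support them.
- A reader might infer that renal function is certainly unmonitored during treatment. Appendix 1 was not available, the opening line of 6.6.1 could be read more widely, and unscheduled tests remain possible.
- A reader might infer that a finding would always come too late to stop dosing. If the final visit falls on Days 75 to 89, some treatment can remain, up to about 15 days.
- A reader might infer that NE3107 endangers the kidneys. An entry exclusion shows who is kept out, not that the drug is nephrotoxic, and no renal signal is reported.

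**Conclusion.** The point holds as a low-priority safety improvement. On sections 6.6.1, 7.1, 7.3 and 7.5, participants aged 50 to 89 with entry clearance of 45 mL/min or more have about 75 to 90 days on drug with no scheduled renal value. It is neither an internal contradiction nor evidence of harm.

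The conclusion assumes that the sub-headings in 6.6.1 govern which test is done when, and that Appendix 1 does not add creatinine at the interim draws. If Appendix 1 does list it, what remains is a wording mismatch. The 34-day figure also assumes interim draws on Days 14, 28 and 56. Confidence is medium, because both Appendix 1 and the Investigator's Brochure are missing from the supplied text.

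**What to change.** Add serum creatinine, with calculated Cockcroft-Gault clearance, to the week 2, 4 and 8 list in section 6.6.1, and align Appendix 1 if it differs. The other inputs to the formula are already to hand: age and sex are recorded at entry, and weight is taken at the week-1 and monthly visits. The sponsor and investigator should decide what change calls for a repeat test or for withdrawal; this point sets no threshold.

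The cost is at most 75 added results on draws and laboratory orders that already exist, with no new visit or procedure. The downside is some follow-up of small changes that prove unimportant. That is more likely because section 6.6.2 lets participants use different clinical laboratories, so a small isolated rise should be repeated before anyone acts on it.
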